## 7 STUDY MEDICATION OVERVIEW AND SAFETY

---

### 7.1 UBLITUXIMAB

---

Chemical Name:	ublrituximab
Other Names:	TG-1101
Classification:	Recombinant chimeric anti-CD20 monoclonal antibody
Mode of Action:	Targets CD20 antigen on B-cells
Description:	Ublrituximab is a genetically engineered chimeric murine/human mAb directed against the CD20 antigen found on the surface of B lymphocytes. Ublrituximab displays the typical structure of immunoglobulins, consisting of two gamma ( $\gamma$ ) heavy chains and two kappa ( $\kappa$ ) light chains linked by disulfide bridges. It is composed of a murine variable region (37.2% of total amino acids) fused onto human constant regions.
How Supplied:	Concentration of 10 mg/mL in 15 mL (150 mg) or 25 mg/mL in 6 mL (150 mg) single-use glass vials.
Storage:	Ublrituximab must be stored in a secured limited-access refrigerated area at a temperature ranging from +2°C / + 8°C. Ublrituximab must not be frozen.
Stability:	Once a vial of ublrituximab has been opened and/or diluted it must be used immediately. After dilution, ublrituximab is stable in static conditions for 24 hours at 25°C, and in dynamic conditions it is stable for 8 hours at 25°C.  Ublrituximab has a shelf-life of 36 months if stored between +2°C / + 8°C, based on stability data.
Route of Administration:	Intravenous
Packaging:	Ublrituximab is packed in kits. Each kit contains: 
 
• Six vials containing 150 mg solution of ublrituximab each or
 
• One vial containing 150 mg solution of ublrituximab (used as replacement, if needed)
 
 
The container closure system for the vials containing 6mL is a type I glass vial closed by a siliconized chlorobutyl rubber stopper sealed with an aqua plastic and aluminum cap.
 
The container closure system for the vials containing 15 mL is a Type I plus borosilicate vial closed by a siliconized bromobutyl rubber stopper sealed with a white plastic and aluminum cap.

Availability:	Ublrituximab is available from TG Therapeutics.

## 7.2 UMBRALISIB (TGR-1202)

---

Classification:	Phosphatidylinositol-3-Kinase (PI3K) Delta Inhibitor
Formulation:	See Investigator Brochure
Mode of Action:	Irreversibly inhibits activity of the Class I Delta isoform of PI3K
How Supplied:	Umbralisib: 200 mg tablets
Storage:	Store at 25°C. Excursions permitted 15°C to 30°C.
Stability:	Retest dates will be provided periodically by Sponsor.
Route of Administration:	Oral
Packaging:	Umbralisib is provided in HDPE bottles each containing 30 tablets and a silica gel canister as a desiccant.
Availability:	Umbralisib is available from TG Therapeutics.

## 7.3 COMPREHENSIVE ADVERSE EVENTS AND POSSIBLE RISKS - UBLITUXIMAB + UMBRALISIB COMBINATION

---

The following adverse events were observed in subjects treated with the combination of ublituximab + umbralisib and were considered at least possibly related to one or both of the study medications. The preliminary safety data as of May 1, 2018 is provided for a total of 75 subjects exposed to ublituximab + umbralisib with a maximum follow up of 3+ years. See [the latest ublituximab and umbralisib Investigator's Brochures](#) for updated safety information a complete list of all adverse events reported regardless of causality.

### 7.3.1 VERY COMMON ( $\geq 10\%$ ):

---

**Blood and Lymphatic System Disorders:** anemia, neutropenia  
**Gastrointestinal Disorders:** diarrhea, nausea, vomiting  
**General Disorders and Administration Site Conditions:** fatigue  
**Injury, Poisoning and Procedural Complications:** infusion related reaction  
**Metabolism and Nutrition Disorders:** decreased appetite

### 7.3.2 COMMON ( $\geq 1\%$ - $< 10\%$ ):

---

**Blood and Lymphatic System Disorders:** thrombocytopenia  
**Cardiac Disorders:** cardiac failure congestive  
**Ear and Labyrinth Disorders:** ear congestion, ear discomfort  
**Eye Disorders:** conjunctival pallor, conjunctivitis, corneal oedema, vision blurred  
**Gastrointestinal Disorders:** abdominal discomfort, abdominal distension, abdominal pain, constipation, dyspepsia, flatulence, gastroesophageal reflux disease, haematochezia, salivary hypersecretion, stomatitis

**General Disorders and Administration Site Conditions:** asthenia, chills, face oedema, infusion site pain, local swelling, oedema peripheral, pyrexia, systemic inflammatory response syndrome

**Hepatobiliary Disorders:** hyperbilirubinaemia

**Immune System Disorders:** hypogammaglobulinaemia

**Infections and Infestations:** bronchitis, cellulitis, clostridium difficile colitis, enterocolitis infectious, oral candidiasis, oral herpes, otitis media, pneumonia, pneumonia streptococcal, rhinovirus infection, sepsis, sepsis syndrome, sinusitis, skin infection, upper respiratory tract infection, urinary tract infection

**Injury, Poisoning and Procedural Complications:** wound

**Investigations:** alanine aminotransferase increased, aspartate aminotransferase increased, blood alkaline phosphatase increased, blood creatinine increased, computerised tomogram thorax abnormal, immunoglobulins decreased, weight decreased

**Metabolism and Nutrition Disorders:** dehydration, failure to thrive, hyperglycaemia, hyperuricaemia, hypokalaemia, hypophosphataemia

**Musculoskeletal and Connective Tissue Disorders:** joint swelling, muscle spasms, muscular weakness, myalgia, pain in extremity

**Nervous System Disorders:** dizziness, dysgeusia, headache, lethargy, sinus headache, somnolence

**Psychiatric Disorders:** agitation, anxiety

**Renal and Urinary Disorders:** micturition urgency, renal failure, renal failure acute

**Reproductive System and Breast Disorders:** scrotal cyst, semen discolouration

**Respiratory, Thoracic and Mediastinal Disorders:** choking, cough, dysphonia, dyspnea, epistaxis, hypoxia, oropharyngeal pain, pneumonitis, productive cough, sinus congestion

**Skin and Subcutaneous Tissue Disorders:** alopecia, cold sweat, dermatitis acneiform, dermatitis bullous, dry skin, ecchymosis, pruritus, rash maculo-papular, rosacea, urticaria

**Vascular Disorders:** hypertension

## 8 MEASUREMENT OF EFFECT

---

During the study period, all subjects will be evaluated for response by CT and/or MRI. Evaluations are to be obtained at approximately cycles 3, 6 and 12. Following cycle 12, evaluations should occur at least every 12 cycles unless clinically indicated more frequently. The determination of response and progression will be based on IWCLL criteria (Hallek M, 2008) by the treating investigator.

CT scan is the preferred method of tumor assessment, but MRI may be used at the investigator's discretion. The same method of assessment and the same technique should be used to characterize each identified and reported lesion at baseline and throughout the study. All baseline assessments to characterize disease will be performed within approximately 45 days of Cycle 1 Day 1, prior to initiation of therapy.

Subjects should remain on study treatment until the occurrence of definitive disease progression, unacceptable toxicity, or withdrawal from the study due to investigator decision or other reasons. Subjects who discontinue from study treatment (either for toxicity or physician choice) and have not progressed will continue to be followed for progression as per the protocol.

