#### 8.2.1 TARGET LESIONS

---

At baseline, up to 6 lymph nodes should be selected as target lesions that will be used to quantitate the status of the disease during study treatment. Ideally, the target lesions should be located in disparate regions of the body. Only peripheral nodes need be selected as target lesions. However, it

is optimal if mediastinal and retroperitoneal areas of disease are assessed whenever these sites are involved.

Target lesions will be measured and recorded at baseline and as per the study assessment schedule. The cross-sectional dimensions (the largest cross-sectional diameter, i.e., the LD × LPD) will be recorded (in cm) for each target lesion. The product of the perpendicular diameters (PPD) (in cm^2) for each target lesion and the sum of the products (SPD) (in cm^2) for all target lesions will be calculated and recorded. The baseline SPD will be used as references by which objective tumor response will be characterized during treatment. The nadir LD of individual lesions and the nadir SPD will be used as references by which CLL progression will be characterized. All LD and LPD diameters will be reported in centimeters and all PPDs and SPDs will be reported in centimeters squared.

A nodal mass may be selected as a nodal target lesion if it is both abnormal and measurable at baseline. A lymph node lesion is considered abnormal if it has a single diameter that is > 1.5 cm and is considered measurable if it has 2 perpendicular diameters that can be accurately measured in cross section with the LD being ≥ 1.0 cm and the LPD also being ≥ 1.0 cm.

A new node that measures >1.5 cm in the LD and >1.0 cm in the LPD will be considered progressive disease.

In cases in which a large lymph node mass has split into multiple components, all subcomponents regardless of size will be used in calculating the SPD. Progression of the lesion will be based on the SPD of sub-components. Lesion sub-components will have the true PPDs calculated. Similarly, lesion sub-components that are visible but neither abnormal nor measurable will have the default PPD of 1.0 cm^2 (1.0 cm × 1.0 cm) used in calculating the SPD.

If lesions merge, a boundary between the lesions will be established so the LD of each individual lesion can continue to be measured. If the lesions have merged in a way that they can no longer be separated by this boundary, the newly merged lesion will be measured bi-dimensionally.

---

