## 8.3 DEFINITIONS OF TUMOR RESPONSE AND PROGRESSION

---

Responses will be categorized as CR, PR, SD, or PD. In addition, a response category of not evaluable (NE) is provided for situations in which there is inadequate information to otherwise categorize response status.

The best overall response will be determined. The best overall response is the best response recorded from the start of treatment until disease/recurrence progression (taking as a reference for disease progression the smallest measurements recorded since treatment started). Where imaging data are available, these data will supersede physical examination data in determining tumor status.

---

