## 8.7 DEFINITIVE DISEASE PROGRESSION

---

The occurrence of any of the following events indicates definitive PD:

- Evidence of any new disease:
  - A new node that measures >1.5 cm in the LD and >1.0 cm in the LPD
  - New or recurrent splenomegaly, with a minimum LVD of 14 cm
  - New or recurrent hepatomegaly, with a minimum LVD of 20 cm
  - Unequivocal reappearance of an extra-nodal lesion that had resolved
  - A new unequivocal extra-nodal lesion of any size
  - \*New non-target disease (e.g., effusions, ascites, or other organ abnormalities related to CLL).

\*Isolated new effusions, ascites, or other organ abnormalities are not sufficient evidence alone of PD unless histologically confirmed. Thus, a declaration of PD should not be made if this is the only manifestation of apparently new disease.

- Evidence of worsening of target lesions, spleen or liver, or non-target disease:
  - Increase from the nadir by  $\geq 50\%$  from the nadir in the SPD of target lesions
  - Increase from the nadir by  $\geq 50\%$  in the LD of an individual node or extra-nodal mass that now has an LD of >1.5 cm and an LPD of > 1.0 cm
  - Splenic progression, defined as an increase in splenic enlargement by  $\geq 50\%$  from nadir (with a minimum 2 cm increase and a minimum LVD of 14 cm)
  - Hepatic progression, defined as an increase in hepatic enlargement by  $\geq 50\%$  from nadir (with a minimum 2 cm increase and minimum LVD of 20 cm)
  - Unequivocal increase in the size of non-target disease (e.g., effusions, ascites, or other organ abnormalities related to CLL)
  - Transformation to a more aggressive histology (e.g., Richter's syndrome) as established by biopsy (with the date of the biopsy being considered the date of CLL progression if the subject has no earlier objective documentation of CLL progression).
- Decrease in platelet count or hemoglobin that is attributable to CLL, is not attributable to an autoimmune phenomenon, and is confirmed by bone marrow biopsy showing an infiltrate of clonal CLL cells
  - The current platelet count is  $< 100 \times 10^9/L$  and there has been a decrease by  $> 50\%$  from the highest on-study platelet count
  - The current hemoglobin is  $< 110 \text{ g/L}$  (11.0 g/dL) and there has been a decrease by  $> 20 \text{ g/L}$  (2 g/dL) from the highest on-study hemoglobin

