## 9.8 EFFICACY ANALYSES

---

All subjects included in the study must have a baseline tumor assessment within 30 days of Cycle 1/Day 1 and at least one post-treatment efficacy evaluation in order to be included in the efficacy analyses. Each subject will be assigned one of the following categories: 1) complete response, 2) partial response, 3) stable disease, 4) progressive disease, 5) early death from malignant disease, 6) early death from toxicity, 7) early death because of other cause, or 9) unknown (not assessable, insufficient data).

---

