## 9.8.2 SECONDARY EFFICACY VARIABLES

---

Progression free survival (PFS) is defined as the time from study entry to the first documentation of tumor progression or death due to any cause whichever comes first. For subjects previously on Arm A of Study UTX-TGR-304, PFS will be calculated from the date of randomization on Study UTX-TGR-304 to the first documentation of tumor progression or death due to any cause whichever comes first. This variable will be analyzed via Kaplan-Meier methodology. The median PFS will be estimated by treatment group, if appropriate (i.e., if sample sizes are sufficient) and overall.

MRD negativity rate is defined as the proportion of subjects who are MRD negative. This variable will be analyzed by the total number and percentage of subjects who are confirmed to achieve MRD negativity as per laboratory confirmation by treatment group and overall.

Duration of response is defined as the time from documentation of a response to treatment to the first documentation of tumor progression or death due to any cause whichever comes first. For subjects previously on Arm A of Study UTX-TGR-304, unless the subject's best overall response during study UTX-TGR-304 was stable disease, the duration of response will be determined from the first documented response on Study UTX-TGR-304. Duration of the response will be summarized using n (sample size), mean, standard deviation, median, minimum and maximum for the responders by treatment group and overall.

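### Arm A's PFS and DOR run from UTX-TGR-304, but the plan sets a new UTX-TGR-204 tumor baseline for everyone and does not say whether Arm A's 304 lesions and nadir carry over

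*Combined protocol and SAP*

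**What the plan says.** **Time origin.** Section 9.8.2 gives Arm A its own rule: "PFS will be calculated from the date of randomization on Study UTX-TGR-304". Arm A's DOR starts at the first response documented in 304, unless the best response there was stable disease.

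**Baseline.** Section 8 has one rule with no exception for Arm A: "All baseline assessments to characterize disease will be performed within approximately 45 days of Cycle 1 Day 1, prior to initiation of therapy". Section 5.1 and footnote 11 of Table 1 also use 45 days. Section 9.8 uses a different window; to enter the efficacy analyses, every subject "must have a baseline tumor assessment within 30 days of Cycle 1/Day 1".

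**Lesions.** Section 8.2.1: "At baseline, up to 6 lymph nodes should be selected as target lesions", and "A lymph node lesion is considered abnormal if it has a single diameter that is > 1.5 cm". Sections 8.2.2 and 8.2.3 likewise take spleen, liver and non-target disease from baseline.

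**Reference for progression.** Section 8.2.1: "The nadir LD of individual lesions and the nadir SPD will be used as references by which CLL progression will be characterized". It does not say in which study the nadir is sought. Section 8.3 refers to "the smallest measurements recorded since treatment started". Section 8.7 requires a rise of at least 50% from nadir for SPD or a node's longest diameter (LD), and measures falls in platelets and hemoglobin from the highest on-study value.

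**Carry-over.** The only stated reuse of 304 tests is for judging eligibility (Table 1, footnote 1).

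**Arm A treatment.** Section 6.1 has Arm A resume treatment at the point reached when 304 ends. Its sentence on 28-day cycles names only Arms B, C and D.

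**Reader.** The treating investigator determines response and progression (Section 8). Table 2, footnote 2, states that there is no central radiology review.

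**The concern.** A fresh baseline suits Arms B, C and D, who enter at confirmed progression and start the combination. Arm A subjects enter non-progressed and already on treatment, and some may be in response. For them the clock is continuous from 304, while the measuring reference, as Section 8 is worded, starts at 204 entry.

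The 50% rules are relative to a nadir, so the choice of nadir decides when progression is declared. Two investigators with identical scans could give different dates if one uses the 304 nadir and the other the 204 entry scan.

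The synopsis makes PFS and DOR the primary objectives for Arm A. No hypothesis is tested, so the descriptive estimates are the whole result. The problem is separate from the 304 lead-in time: starting the clock at 204 entry would not settle which nadir applies.

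**Working it through.** The plan gives no sample size, power or event count that bears on this point, so there is no figure to reproduce. The check applies the protocol's own thresholds.

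**1. SPD threshold.** Let N be the 304 nadir SPD and g the proportional growth from that nadir to 204 entry. By definition of a nadir, g ≥ 0. Arm A entrants must be non-progressing (Section 3.1), so g < 0.5, assuming 304 uses the same 50% rule and the same nodes are followed.

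- 304 nadir carried forward: progression at 1.5 × N.
- Reference reset at entry: progression at 1.5 × (1 + g) × N.

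| g | Threshold after reset | Rise over 304 nadir |
|---|---|---|
| 0 | 1.5 × 1.00 = 1.500 N | +50% |
| 10% | 1.5 × 1.10 = 1.650 N | +65% |
| 25% | 1.5 × 1.25 = 1.875 N | +87.5% |
| 40% | 1.5 × 1.40 = 2.100 N | +110% |
| limit, 50% | 1.5 × 1.50 = 2.250 N | +125% (not reached) |

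Example: nadir 4.0 cm², entry 5.6 cm² (5.6 / 4.0 = 1.40, not progression). Progression is at 1.5 × 4.0 = 6.0 cm² if the nadir carries forward, and at 1.5 × 5.6 = 8.4 cm² if it is reset.

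**2. Other rules from nadir.**

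- Node LD: nadir 2.0 cm, entry 2.8 cm. Progression at 1.5 × 2.0 = 3.0 cm or 1.5 × 2.8 = 4.2 cm.
- Spleen (enlargement is the length above 12 cm; minimum increase 2 cm): nadir 15 cm has 3 cm of enlargement. Half of that is 1.5 cm, so the 2 cm minimum applies and progression is at 17 cm. Entry at 16.9 cm has 4.9 cm of enlargement; half is 2.45 cm, so a reset puts progression at 16.9 + 2.45 = 19.35 cm.

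**3. The direction can reverse.** A node that regressed to 1.3 cm cannot be a 204 target, because it must exceed 1.5 cm. Against its 304 nadir the LD rule is met at 1.5 × 1.3 = 1.95 cm. If an investigator reads it as new in 204, progression is declared once LD exceeds 1.5 cm with the perpendicular diameter above 1.0 cm, which is earlier.

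**4. Complete responders.** Section 8.4 requires every target node to be at most 1.5 cm, so none qualifies as a 204 target and the SPD rule has no reference. The new-node, recurrent spleen or liver enlargement and extra-nodal rules still operate.

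**5. Delay in time, as an illustration.** Assume exponential growth with doubling time T. The extra time to the SPD threshold is T × log2(1 + g). The documents give neither T nor g.

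| g | T = 6 months | T = 12 months | T = 24 months |
|---|---|---|---|
| 0 | 0 | 0 | 0 |
| 10% | 0.8 | 1.7 | 3.3 |
| 25% | 1.9 | 3.9 | 7.7 |
| 40% | 2.9 | 5.8 | 11.7 |

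After cycle 12, scans may be 12 cycles apart: 12 × 28 = 336 days, or 336 / 30.4375 = 11.0 months. A threshold just missed at one scan can therefore move the recorded date by about 11 months, unless a scan is clinically indicated sooner.

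**The case against.** A reader might infer that the protocol discards the 304 nadir and target nodes for Arm A and so biases PFS and DOR upward. The documents do not support that as a stated rule or as a general result.

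- No section says the 304 values are dropped. Section 8.3 counts from the start of treatment, which for Arm A was in 304. Section 8 places baseline before therapy begins, which a 204 entry scan in a subject already on treatment cannot satisfy. Section 6.1 treats Arm A's therapy as continuous.
- Only 304 sites take part (Section 4.3), so earlier scans should be within reach. Appendix A counts a 50% increase in the diameter of any previous site, without limiting it to lesions chosen at 204 entry.
- Later progression is conditional. It is zero at g = 0, the 2.25-fold figure is an upper limit, other rules may trigger first, and the direction can reverse.
- PFS and DOR are primary for Arm A only in the synopsis; Sections 2.1 and 9.8 make ORR primary. The 304 clock is explicit only in Section 9.8.2; the synopsis starts PFS at enrollment and Section 2.2 at randomization.

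All of this stands, and it limits the claim. It does not remove the gap. The plan writes explicit Arm A exceptions for the time origin and for treatment, but none for baseline, lesion selection or nadir. Two tenable readings, with no central review, are what allow different dates from the same scans. If carry-forward is intended, nothing says which 304 values apply or where they come from.

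**Conclusion.** The point holds as a mismatch between stated rules. Arm A's time origin lies in 304, while the baseline and lesion rules, read as worded, place the reference in 204, and no text links the two.

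If the reference is reset, the SPD threshold moves from +50% to between +50% and just under +125% over the 304 nadir. Progression is dated late in subjects already regrowing at entry, is unchanged in those at nadir, and may be dated early where a regressed node is taken as new.

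These figures assume that 304 uses the same 50% rule and that the same nodes are followed. The delays in months also rest on assumed doubling times. The documents give no distribution of regrowth at entry, so neither the size nor the sign of the net effect on median PFS or DOR can be computed. The gap should be closed because the correction is cheap and these estimates are the headline for Arm A in the synopsis.

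**What to change.** In Sections 8.2.1, 8.3, 8.7 and 9.8, state that:

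1. For subjects from Arm A, the 304 target and non-target lesions, baseline, nadir (SPD, LD, and spleen and liver longest vertical dimension) and highest platelet and hemoglobin values carry forward. The 204 entry scan is a follow-up time point.
2. The new 204 baseline, and the Section 9.8 condition tied to Cycle 1 Day 1, apply to Arms B, C and D only.
3. The carried-forward values are the 304 investigator's measurements, to match investigator assessment in 204 and avoid mixing readers.
4. One baseline window applies throughout, replacing the present 45 and 30 days.

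The synopsis and Section 2.2 should give the same Arm A time origin as Section 9.8.2.

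**Cost.** Protocol wording, eCRF fields and transfer of existing 304 measurements; no extra scans. This assumes that lesion-level investigator values from 304 can be retrieved, which the documents do not show. Arm A PFS and DOR may come out shorter than under a reset reference.
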